4.6 Per Protocol Population

The PP Population is defined as the subset of subjects in the ITT Population who do not have any major protocol deviations that could affect the efficacy analyses of the

double-blind data. An analysis of the primary and secondary efficacy variables for the PP Population will be performed.

The PP Population is defined as subjects who:

- Received at least 80% of the planned study drug doses while in the study
- Received at least one study dose in each of Week 11 and 12 of the Double-blind period, if present through Week 12
- Did not receive a different treatment than the treatment to which they were randomized
- Had a mean baseline Worst Itching Intensity NRS score >4.0
- Had a non-missing average 24-hour weekly Worst Itching Intensity NRS score available for at least 75% of study weeks while in the study (weeks with >3 missing daily values are considered missing)
- Did not have significant amounts of restricted and prohibited medications listed in protocol Section 6.4.9 based on medical review.
- Did not have other major protocol violations that would impact efficacy outcomes

Prior to unblinding, the protocol violations and medications will be reviewed in a blinded manner and the PP Population will be determined. Subjects will be analyzed in the treatment arm to which they were randomly assigned regardless of which treatment they received.

5. STUDY SUBJECTS

5.1 Disposition of Subjects

The number of subjects who enrolled, failed screening, were randomized, received treatment, completed treatment, and discontinued from treatment, along with the reason for discontinuation, and number of subjects who entered the Open-label Treatment Period will be presented by treatment group and overall for the Double-blind Treatment Period. Additionally, the number of subjects who entered the Discontinuation Period, completed and discontinued from the Discontinuation Period and the reason for discontinuation will be reported. Subjects randomized will also be reported by the randomization stratification factors.

The following provides the definitions of the aforementioned groups:

- Enrolled subjects are all subjects who sign informed consent.
- Randomized subjects consist of all screened subjects who have a randomization record in the interactive voice/web randomization system.
- Treated subjects are all subjects who received at least one dose of double-blind study drug.
- Subjects who completed treatment are those randomized subjects with a “Yes” noted for the question “Did the subject complete the Double-blind Treatment Period?”.
- Subjects who discontinue treatment early are randomized subjects with “No” noted for the question “Did the subject complete the Double-blind Treatment Period?”. Reasons for treatment discontinuation are also collected on this case report form (CRF).
- Subjects who entered the Discontinuation Period are those who have at least one visit during the Discontinuation Period.
- Subjects who complete the Discontinuation Period are those who have a visit for Day 12 of the Discontinuation Period recorded or were marked as “Yes” to the CRF question “Did the subject complete the whole Double-blind phase of study? (Screening through Discontinuation Period)”
- Subjects who discontinue from the Discontinuation Period are those who entered the Discontinuation Period but do not meet the Discontinuation Period completion criteria above.
- Subjects who entered the Open-label Treatment Period are those who received at least one dose of study drug in the Open-label Treatment Period.

For all categories of subjects (except for enrolled subjects and screen failures), percentages will be calculated using the number of randomized subjects as the denominator.

Additionally, the analysis populations will be summarized in a table by subject counts, as well as in a subject listing:

- Intent-to-treat Population;
- Double-blind Safety Population;
- Double-blind Discontinuation Population;
- Double-blind Discontinuation Safety Population;
- Per Protocol Population

The reasons for exclusion from the PP Population will also be summarized in a table by subject counts. Percentages will be calculated using the ITT population as the denominator.

5.2 Protocol Deviations

Protocol deviations will be identified in several ways: through programmatic checks, through medical reviews, and by clinical research associates during site monitoring. Deviations will be classified as minor or major prior to the database lock. Protocol deviations will be summarized by treatment group. All protocol deviations will be listed.

6. DEMOGRAPHIC AND OTHER BASELINE CHARACTERISTICS

Demographic and baseline characteristics will be collected during the Screening Visit.

Descriptive statistics will be provided for all demographic and baseline characteristics based on the Double-blind Safety Population. For categorical variables, the number and percentage of subjects in each category will be presented. For continuous variables, summaries will include the number of subjects with data, mean, median, standard deviation, minimum, and maximum.

All demographic and other baseline characteristics will be provided in a listing.

6.1 Demographic Characteristics

Demographic and baseline variables will be summarized by treatment group and include the following:

- Age at screening (years) as recorded on the CRF
- Age category at screening (<45, ≥ 45-<65, 65-<75, ≥75)
- Gender
- Ethnicity
- Race
- Prescription dry body weight (kg)

6.2 Baseline Disease Characteristics

Baseline characteristics of the disease will also be summarized by treatment group and include the following:

- Duration of pruritus (years)
- Years since ESRD
- Years since chronic kidney disease (CKD)
- Years on chronic hemodialysis
- Etiology of CKD
- Baseline Worst Itching Intensity NRS
- Anti-itch medication use during the Run-in Period (stratification factor)
- Presence of specific medical conditions (stratification factor)

Duration of pruritus (years) will be calculated as:

(Date of the Screening Visit – the start date of the pruritus+ 1)/365.25.

Years since ESRD will be calculated as:

(Date of the Screening Visit – first date of ESRD+ 1)/365.25.

Years since CKD will be calculated as:

(Date of the Screening Visit – first date of CKD+ 1)/365.25.

Years on chronic hemodialysis will be calculated as:

(Date of the Screening Visit – date of first chronic hemodialysis + 1)/365.25.

For each of the above, if partial dates are recorded, the first day of the month will be imputed for missing day, and January for missing month.

6.3 Medical History

Medical history data consisted of a fixed list of conditions to be checked off and any additional self-reported medical conditions not contained on the list. Both types of medical history will be coded using Medical Dictionary for Regulatory Activities (MedDRA); however, the pre-specified medical history will use the fixed list of conditions as preferred terms and map to the most appropriate system organ class (SOC) based on MedDRA and blinded medical review. Medical history terms that were not pre-specified will be coded for SOC and preferred term. Both types of conditions (selected from the fixed list or self-reported) will be combined and summarized by MedDRA SOC, preferred term, and treatment group. Both types of conditions will also be reported together for separate summaries of conditions related to dialysis, conditions worsening during dialysis, and conditions not related to dialysis. The data will also be listed, including the verbatim investigator description of the relevant medical condition, the coded terms (SOC, preferred term), start date, end date, and whether or not the condition is ongoing.

A separate coding listing will be created with all the distinct levels of SOC, preferred terms, and the verbatim investigator description reported in the study. Sorting will be alphabetically by SOC, preferred term, and then verbatim description.

6.4 Prior and Concomitant Medications

All medications, including any antipruritic medications, taken during the 3 months prior to the first dose of study drug on Day 1 through the end of the Double-blind Treatment Phase or early termination (i.e., End-of-Treatment/Early Termination Visit) will be recorded.

These will be coded using the March 2018 World Health Organization Drug Dictionary Enhanced plus Herbal Dictionary. All prior and concomitant medications will be listed. Additionally, a listing for unique medications and their corresponding coding will be presented.

6.4.1 Prior Medication

Prior medications (including vitamins and herbal supplements) are defined as medications collected on the *Previous or Concomitant Medications CRF page* that the subject has taken any time during the last 3 months prior to the first dose of study drug on Day 1 of the Double-blind Treatment Period. Prior medications will be summarized in a table by treatment group using the Double-blind Safety Population. Medications will be reported by drug class (Anatomical Therapeutic Chemical [ATC] Level 3) and ingredient; a subject will be counted only once for each medication.

6.4.2 Concomitant Medication

Concomitant medications used during the Double-blind Treatment Period are medications taken from after the first dose of study drug on Day 1 of the Double-blind Treatment Period through the End-of-Treatment or Early Termination Visit. Concomitant medications during the Double-blind Treatment Period will be summarized by treatment group for the Double-blind Safety Population. Medications will be reported by drug class (ATC Level 3) and ingredient; a subject will be counted only once for each medication.

Concomitant medications used during the Discontinuation Period are medications taken from after the start of the Discontinuation Period through up to 2 weeks after the start of the Discontinuation Period or the start of the Open-label Treatment Period, whichever comes first. Concomitant medications used during the Discontinuation Period will be summarized for the Double-blind Discontinuation Safety Population.

6.4.3 Anti-Itch Medication

Anti-itch medications are identified as medications where “Yes” is checked on the *Previous or Concomitant Medications CRF page* to the question “Medication was given to treat pruritus.”

The prior and concomitant medication summaries described in Sections [6.4.1](#) and [6.4.2](#) will be repeated for the anti-itch medications, but presented by ingredient (and not ATC level 3). Concomitant medications during the double-blind Treatment Period and Discontinuation Period will be summarized separately.

7. STUDY DRUG EXPOSURE AND TREATMENT COMPLIANCE

For this study, the duration of double-blind treatment for each individual subject is expected to be 12 weeks, for a total of approximately 36 doses of study drug administered immediately following each dialysis session.

The following variables will be summarized by treatment group to describe the duration of exposure and length of participation in the Double-blind Treatment Period:

- Duration of double-blind treatment (days) as: (Date of first dialysis after last dose) – (Date of first double-blind dose) + 1.
- Duration of double-blind phase (days), from first double-blind dose to final assessment in the discontinuation period. This will be (End of double-blind participation date, including Discontinuation Period) – (Date of first double-blind dose) + 1.
- Average dose per administration (mcg/kg)

The following measures will be used to assess compliance:

- Total number of double-blind doses actually received (1-3, 4-6, 7-9, etc.)
- Total number of dialysis visits logged (1-3, 4-6, 7-9, etc.)
- Number of missed doses
- Number of missed dialysis visits
- Number of subjects with extra doses
- Number of subjects with extra dialysis visits

If a subject receives additional dialysis during a given week for any reason, an additional dose of CR845 will be administered following dialysis. A maximum of 4 doses per week is allowed. No additional doses will be given for subjects receiving an additional unscheduled ultrafiltration treatment. The number of subjects getting such an extra treatment will be summarized.

Missed and extra doses/dialysis will be determined as follows:

1. Individual weeks for each subject are examined.
2. Each subject should have 3 doses per week up to the final week of the period. Anything more will be counted as extra doses; anything less will be counted as missed doses.
3. Subjects who do not complete through the final week of the period will be checked for how far they were into the week that they discontinued: 1,2 days means that they should have 1 dose; 3,4 = 2 doses; 5 or more = 3 doses. This will be compared to actual doses for that week to determine missed/extra.
4. The missed and extra doses are then summed across each subject's weeks to get the total missed and extra.

8. EFFICACY EVALUATION

8.1 Overview of Efficacy Analysis Issues

8.1.1 Handling of Dropouts or Missing Data

A variety of approaches will be applied for subjects that have missing Week 12 averages of daily Worst Itching Intensity NRS; full details of these for both the primary analysis and sensitivity analyses may be found in Section [8.2](#).

Note that a subject must report at least 4 values for a week in order for the weekly mean of the 24 hour Worst Itching Intensity NRS to be non-missing.

Handling of missing data for other endpoints is discussed in the specific sections for those endpoints.

8.1.2 Multicenter Studies

The Week 12 change from baseline will be reported in a separate display with summary statistics by site; likewise, the counts and proportions (out of the ITT Population at that site) of subjects achieving ≥ 3 -point improvement from baseline will be reported by site (for sites that have at least two subjects in each treatment with data present at week 12). Otherwise, data from all sites will be pooled for the purpose of analyses.

8.1.3 Multiplicity Handling

The efficacy of CR845 0.5 mcg/kg compared to placebo in pivotal phase 3 study CLIN3102 will be evaluated based on 1 primary and 3 secondary efficacy endpoints.

Testing of the primary efficacy endpoint will be 2-sided and conducted at the 5% error level. The study will be considered positive if the null hypothesis of no treatment difference in the primary efficacy analysis of the primary endpoint (proportion of subjects achieving ≥ 3 -point improvement from baseline with respect to the Worst Itching Intensity NRS at Week 12 of the Double-blind Treatment Period) is rejected in favor of the alternative that subjects randomized to CR845 experience significantly less itching compared to subjects randomized to placebo.

To protect the Type 1 error, a gate-keeping strategy will be implemented. Although the p-values corresponding to the hypothesis testing of the secondary variables will be reported, they will only be considered inferential if the primary analysis is statistically significant. Testing of the 3 secondary efficacy endpoints will be performed sequentially at a 2-sided 5% error level. The difference between CR845 0.5 mcg/kg and placebo with respect to the 5-D Itch total score will be tested first using the ANCOVA approach in section [8.2.4.3](#). If results are statistically significant in favor of CR845, testing with respect to the Skindex-10 total score will be conducted, also using ANCOVA. The proportion of subjects achieving ≥ 4 -point improvement from baseline with respect to the weekly mean of the daily 24-hour Worst Itching Intensity NRS at Week 12 of the

Double-blind Treatment Period will be tested only if the results of Skindex-10 total score are statistically significant in favor of CR845.

8.2 Efficacy Variables

[Table 3](#) presents a summary of the study efficacy variables and types of analyses used to evaluate them.

Table 3 Efficacy Variables and Analysis Methods

Efficacy Variables	Analysis Methods			
	ANCOVA	MMRM	Logistic Regression	CMH
Primary				
≥3-point improvement from baseline in Worst Itching Intensity NRS at Week 12 of the Double-blind Treatment Period			X	
Secondary				
Change from baseline in 5-D Itch Scale score at Week 12 of the Double-blind Treatment Period	X	X		
Change from baseline Week 12 in total Skindex-10 Scale score at Week 12 of the Double-blind Treatment Period	X	X		
≥4-point improvement from baseline in Worst Itching Intensity NRS at Week 12 of the Double-blind Treatment Period			X	
Other Efficacy Variables				
Itch-intensity Variables				
>0-, ≥1-, ≥2-, ≥3-, ≥4-, ≥5-, ≥6-point improvement from baseline in Worst Itching Intensity NRS at Week 12 of the Double-blind Treatment Period			X	
≥3-point improvement from baseline in Worst Itching Intensity NRS at Week 12 of the Double-blind Treatment Period by the stratification variables			X	
Change from baseline in the weekly mean of the 24 hour Worst Itching Intensity NRS score at each week of the Double-blind Treatment Period		X		
Proportion of subjects with “Very Much Improved” or “Much Improved” on Patient Global Impression of Change at Week 12 of the Double-blind Treatment Period				X
Worst Itching Intensity NRS Complete Responder			X	
Itch-related Quality-of-Life Variables:				
Change from baseline in total Skindex-10 Scale score, at each week		X		
Change from baseline in each of the three Skindex-10 Scale Scores, at each week	X	X		
≥15-point improvement from baseline in total Skindex-10 Scale score, at each week			X	
Change from baseline in the total 5-D Itch Scale, at each week		X		
Change from baseline in the five 5-D Itch Scale domains, at each week	X	X		
≥5-point improvement from baseline in total 5D Itch Scale, at each week			X	

ANCOVA = analysis of covariance; CMH = Cochran-Mantel-Haenszel exact test; MMRM = mixed effects model with repeated measures; NRS = numerical rating scale

8.2.1 Primary Efficacy Endpoint

The primary efficacy endpoint is defined as the proportion of subjects achieving ≥ 3 -point improvement from baseline with respect to the weekly mean of the daily 24-hour Worst Itching Intensity NRS at Week 12 of the Double-blind Treatment Period.

Intensity of itch will be measured using the Worst Itching Intensity NRS (see protocol Appendix 2) on a worksheet in which subjects will be asked to indicate the intensity of the worst itching they experienced over the past 24 hours by marking 1 of 11 numbers, from 0 to 10, that best describes the intensity, where “0” is labeled with the anchor phrase “no itching” and “10” is labeled “worst itching imaginable.” Subjects will be provided with these worksheets to record their 24-hour worst itching assessment scores, both at the clinic on dialysis days and at home on non-dialysis days.

The weekly mean of the 24-hour Worst Itching Intensity NRS score will be defined as the sum of the daily Worst Itching Intensity NRS scores reported during a specific week during the Double-blind Treatment Period (e.g., Days 2 to 8, Days 9 to 15, Days 16 to 22) divided by the number of days with non-missing scores for that week. If the daily worst itching score is missing for >3 days during a specific week, the corresponding weekly mean worst itching score will be set to missing. Additionally, subjects who discontinue treatment but continue on study and report NRS scores will have their NRS scores censored following discontinuation of treatment; missing data rules will apply to these censored values as though they had missing values/ dropped out from the study entirely.

The baseline score will be defined as the average of the daily 24-hour Worst Itching Intensity NRS scores collected over the Run-in Period, including pre-randomization assessments collected on Day 1. As defined in the protocol, to be randomized, subjects had to report at least 4 non-missing Worst Itching Intensity scores from the start of the 7-day Run-in Period up to and including the pre-randomization assessment on Day 1. For subjects who deviated from the protocol and were randomized with more than 4 missing Worst Itching Intensity NRS scores during the 7-day Run-in Period, the baseline Itch NRS scores will be calculated using all available non-missing scores collected prior to and including the pre-randomization assessment on Day 1. These subjects will be included in the ITT population and excluded from the Per-Protocol population.

8.2.2 Primary Efficacy Analysis

In the primary efficacy analysis, missing NRS data at the end of Week 12 will be imputed using a multiple imputation (MI) approach, assuming that subjects who discontinue double-blind treatment early would have similar Worst Itching Intensity NRS scores as other subjects in their respective treatment arm who have complete data:

- Intermittent missing NRS scores will first be imputed using the Markov Chain Monte Carlo (MCMC) method implemented with the SAS MI procedure, which is appropriate for non-monotonic missing data.
- The monotone missing NRS values will then be multiply imputed with the SAS MI procedure using the monotone regression method.

- For each stage, MI will be performed within treatment group with covariates for baseline NRS score, both randomization stratification factors, and the non-missing NRS scores for each week. Should convergence issues occur due to small cell size for the categorical covariates at either stage, those covariates will be removed from the model.
- The proportion of subjects who have an improvement from baseline with respect to the weekly mean of the daily 24-hour Worst Itching Intensity NRS score ≥ 3 points will be calculated for each imputed dataset. Differences between CR845 0.5 mcg/kg and placebo with respect to the primary endpoint will be compared using a logistic regression model containing terms for treatment group, baseline NRS score, use of anti-itch medication during the week prior to randomization, and presence of specific medical conditions.
- Twenty imputations will be performed.
- Results of the logistic regression on the multiply imputed data sets will be summarized by the SAS MIANALYZE procedure.

The observed number and proportion of subjects with ≥ 3 -point improvement among the non-imputed data will be reported along with the imputed data logistic regression model-based estimates of the proportions of responders, odds ratio, 95% confidence intervals (CIs), and p-value.

Sample size adjustment

The above MI process will be implemented completely independently among subjects contributing the interim results and those following the interim analysis. Likewise, the logistic regression and results described above will be generated independently for both samples, with the samples combined and adjusted as follows:

The final p-value will be calculated using the Cui, Hung, Wang (CHW) procedure where the z-score is a weighted average of the z-score at the interim and the z-score observed for data collected after the interim, following the formula below:

$$Z_{CHW} = Z_{interim} * \sqrt{(n/N)} + Z_{post-interim} * \sqrt{(1 - n/N)}$$

where n is the number of randomized subjects at the interim and N is the initial number of subjects planned (350).

The adjusted odds ratio estimate prior to exponentiating and the 95% CI will be obtained using methodology suggested by Hung and Lawrence:

$$\hat{\delta} = \frac{r_1 \hat{\delta}^{(1)} + \sqrt{1 - r_1} \sqrt{N^* - r_1} \hat{\delta}^{(2)}}{r_1 + \sqrt{1 - r_1} \sqrt{N^* - r_1}}$$

where

$r_1 = n/350$

$N^* = (\text{Re-estimated total sample size})/350$

$\hat{\delta}^{(1)}$ = Least square mean difference from stage 1 analysis

$\hat{\delta}^{(2)}$ = Least square mean difference from stage 2 analysis

$$95\% \text{ CI} = \hat{\delta} \pm \left(\frac{\hat{\delta}}{Z_{CHW}} * 1.96 \right)$$

Note that it is possible for Z_{CHW} and δ to have opposite directions, particularly when close to zero, in which case the absolute value of the ratio will be used in the above formula.

See Section [11](#) for further details on the interim analysis.

The primary analysis and each sensitivity analysis will also be performed using the full combined dataset with the missing data imputed separately for interim subjects and post-interim subjects. No CHW adjustment will be conducted. Presentation of results will start with these analyses (additionally including the CHW results) and then follow with the results of the analysis from each individual stage.

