4.2.2 Safety in Hemodialysis Patients

A review of the aggregate safety data shows that CR845 was well tolerated in hemodialysis patients when administered after each dialysis session for up to 8 weeks at IV doses ranging from 0.5 mcg/kg to 6 mcg/kg. Although patients exposed to CR845 reported more adverse events compared with placebo patients, most events were mild or moderate in nature. Generally mild, transient paresthesias (facial tingling) and/or hypoesthesias (in different anatomic locations), mostly on the first week of dosing, as well as headache, dizziness, and somnolence, were the most frequently reported adverse events associated with CR845 administration. Of note, side effects (eg, dysphoria and hallucinations) commonly associated with centrally-acting kappa opioids were not reported in patients exposed to CR845. Consistent with its lack of affinity for mu-opioid receptors, CR845 did not cause euphoria, respiratory depression, or reduction in oxygen saturation.

CR845-CLIN2101 (Part A) evaluated the safety, pharmacokinetics, and efficacy of repeated IV doses of CR845 compared to placebo over an 8-week treatment period in 174 hemodialysis patients. This study is the longest treatment period evaluated to date in hemodialysis patients and no clinically important or significant safety findings related to CR845 were noted. As expected with patients on hemodialysis, a significant number of the reported serious adverse events (SAEs) were considered not treatment-related, but related to the disease and/or comorbid conditions. There were 31 (17.8%) of 174 patients randomized and treated in the study who had treatment-emergent SAEs. Of the 31 SAE reports, 4 (9%) occurred in 45 placebo-treated patients and 27 (21%) in 129 CR845-treated patients. Only 1 SAE of mental status changes (moderate in severity) in a patient who received CR845 1.5 mcg/kg IV was considered by the Investigator to be probably related to study drug. However, based on the Sponsor's medical review, an alternate etiology of urgent/emergent hypertension offers a more plausible explanation for the acute change in mental status. There were 4 patient deaths (2.3%) in the study, all of which were considered not related to the study drug.

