4.2 Intent-to-treat Population

The ITT Population is defined as the group of subjects who are randomized to a treatment group. Following the ITT principle, subjects in the ITT Population will be analyzed according to their randomized treatment, regardless of the actual treatment received. The ITT population will be used to analyze all efficacy endpoints collected during the double-blind phase.

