The proportion of subjects achieving ≥ 4 -point improvement from baseline with respect to the weekly mean of the daily 24-hour Worst Itching Intensity NRS at Week 12 of the Double-blind Treatment Period will be analyzed following a methodology identical to the one employed for the primary analysis of the primary endpoint (see section 8.2.2). The same dataset will be utilized; separate flags for various cut points of improvement will be utilized to facilitate these analyses. The analysis will be completed for both the ITT and PP Populations.

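### The primary imputation makes no exception for death, so a patient who dies before a Week 12 itch mean is observed can be counted as a responder in the primary and ≥4-point analyses.

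*SAP*

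**What the plan says.** - **Population.** SAP 4.2: "The ITT Population is defined as the group of subjects who are randomized to a treatment group". A patient who dies after randomization stays in the efficacy analysis.
- **Scores after stopping.** Under SAP 8.2.1, scores reported after treatment stops are censored, and "missing data rules will apply to these censored values as though they had missing values/ dropped out from the study entirely".
- **Assumption.** SAP 8.2.2 imputes missing Week 12 scores "assuming that subjects who discontinue double-blind treatment early would have similar Worst Itching Intensity NRS scores as other subjects in their respective treatment arm".
- **Imputation.** SAP 8.2.2 fills intermittent gaps first. Then: "The monotone missing NRS values will then be multiply imputed with the SAS MI procedure using the monotone regression method". On the model: "MI will be performed within treatment group with covariates for baseline NRS score, both randomization stratification factors, and the non-missing NRS scores for each week". The reason for stopping plays no part.
- **Classification.** "Twenty imputations will be performed", and responder status is read from the completed score in each dataset before the logistic model. The Protocol's Statistical Appendix (15.0) describes the same sequence. The sample code in SAP 14 runs on the ITT set by treatment, with no variable or exclusion for death.
- **≥4-point endpoint.** This is the last test in the alpha-controlled sequence (SAP 8.1.3). Under SAP 8.2.4.3 it "will be analyzed following a methodology identical to the one employed for the primary analysis of the primary endpoint", from the same imputed dataset.
- **Death elsewhere.** Neither document gives death a rule for these endpoints; it is dealt with as a safety outcome (for example SAP 9.2 and 9.3).
- **Deaths are foreseeable.** Protocol 4.2.2, on the 174-patient Phase 2 study: "There were 4 patient deaths (2.3%) in the study, all of which were considered not related to the study drug".

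**The concern.** For a patient who withdraws, the Week 12 score exists in principle and is unobserved, so a missing-at-random assumption can be debated. For a patient who has died there is no Week 12 score, and the assumption has no meaning. The plan nevertheless produces a value and lets it qualify as a response.

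At stake is what the headline proportions, odds ratio and p-value describe. They would include some responses assigned to people who died, in the primary analysis and in one alpha-controlled secondary. The SAP is also not uniform: for the complete-responder endpoint (SAP 8.2.5.1), anyone who drops out before Week 12 is a non-responder.

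**Working it through.** **1. Does the rule reach deaths?** ITT is everyone randomized; death ends study drug; later weeks are monotone missing; all monotone missing values are imputed; response is read from the result. No step removes a death. The one exception is a patient who dies within Days 79–85 after at least four daily scores, whose Week 12 mean is observed. If a patient's chance of response in each dataset were the arm rate, the chance of being a responder in at least one of 20 is 1 − 0.7^20 = 99.92% at 30%, and 1 − 0.5^20, above 99.99%, at 50%.

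**2. Reproduce the planned power.** Inputs from SAP 2.6: 175 per arm, placebo 30%, CR845 50%, two-sided 5%, continuity-corrected chi-square.

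Power = Φ[(d − 1/n − 1.96·se0)/se1], where se0 = √(2·p̄(1−p̄)/n), p̄ is the mean of the two rates, and se1 = √((p1(1−p1) + p2(1−p2))/n).

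For 30% v 50%: se0 = √(2 × 0.40 × 0.60/175) = 0.05237; se1 = √((0.21 + 0.25)/175) = 0.05127; z = (0.20 − 0.00571 − 0.10265)/0.05127 = 1.787; power 96.3% (stated 96%). For CR845 rates of 48%, 46% and 45% the formula gives 92.0%, 84.8% and 79.9% (stated 92%, 84%, 79%). The planned figures reproduce.

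**3. A death rate.** The documents give none for this trial. Assumption: the Phase 2 figure applies to that study's 8-week treatment period and scales with time. 4/174 = 2.30%; × 12/8 = 3.45%; × 175 = 6.0 deaths per arm, about 12 in 350. Range shown: 1% to 5%.

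**4. Imputed responders among the deaths.** If the imputed response probability equals the planned arm rate: CR845 6.03 × 0.50 = 3.0; placebo 6.03 × 0.30 = 1.8. This is a simplification, because the model also uses the patient's own earlier scores.

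**5. Count those deaths as non-response.** Multiply each arm's rate by (1 − q), where q is that arm's death rate, and recompute power at 175 per arm.

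| Planned rates | Death rate | Difference (points) | Power |
|---|---|---|---|
| 30% v 50% | none | 20.0 | 96.3% |
| 30% v 50% | 1% each arm | 19.8 | 96.0% |
| 30% v 50% | 3.45% each arm | 19.3 | 95.3% |
| 30% v 50% | 5% each arm | 19.0 | 94.8% |
| 30% v 45% | none | 15.0 | 79.9% |
| 30% v 45% | 3.45% each arm | 14.5 | 77.5% |
| 30% v 50% | 5% CR845, 2% placebo | 18.1 | 92.4% |
| 30% v 45% | 5% CR845, 2% placebo | 13.4 | 70.4% |

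At 3.45%, the arm rates fall by 0.0345 × 50 = 1.7 points and 0.0345 × 30 = 1.0 point, a net 0.7 on the difference. The unequal rows are illustrations, since the documents do not give deaths by arm.

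**6. What the sensitivity analyses cover (SAP 8.2.3).**
- Sensitivity 1 makes everyone who stops drug early a non-responder, which should include these deaths.
- Sensitivity 2 draws adverse-event discontinuers from a baseline distribution trimmed at 4 to 10. The SAP does not say whether death counts as such a discontinuation. Even if it does, a draw of 4 is still a response when baseline is 7 or more.
- Sensitivity 3 shifts missing Week 12 scores in the CR845 arm by up to 5 points.
- All three are specified for the primary endpoint. None is named for the ≥4-point endpoint.

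**The case against.** The case for leaving the plan alone has four parts.

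**No false benefit.** A reader might infer that the arm with more deaths is credited with imputed improvement. The documents do not support that. Within-arm imputation gives a patient who died roughly the arm's own response probability, adjusted for baseline, strata and earlier scores, so the arm's rate stays about where it was however many die. Someone not improving before death would get a lower predicted response than average. The shifts in the table arise only by comparison with a rule that counts death as non-response. This stands: the defect is a missing penalty, not a reward.

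**No sign of unequal deaths.** It is tempting to read the Phase 2 serious adverse event rates (21% CR845, 9% placebo) as a warning of excess deaths on CR845. They are not death rates; they pool three doses of which this trial uses one; and 27/129 v 4/45 gives a Fisher p of 0.07. All four deaths were considered unrelated to drug. This also stands.

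**The death rate is soft.** Protocol 4.2.2 does not tie the four deaths to the 8 treatment weeks. The exact 95% interval for 4/174 is 0.6% to 5.8%, or about 3 to 30 deaths in 350 after the same scaling. The figure of 12 is an order of magnitude only.

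**The primary endpoint is already stressed.** Sensitivity 1 and 3 address this scenario, and the SAP also reports observed, non-imputed responder proportions. That largely protects interpretation of the primary result. It does not settle the matter, because the confirmatory test still rests on the imputed responses and the ≥4-point endpoint has no named sensitivity analysis.

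**Conclusion.** The point holds in a limited form. By its stated rule, the plan can count a patient who has died as a responder in the confirmatory primary analysis and in the ≥4-point analysis. That is a result without meaning for those patients, and death should have an explicit strategy.

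The expected size is small: about 0.7 points on a 20-point difference and 1.0 point of power, with power between 96.0% and 94.8% for equal death rates of 1% to 5%. This rests on the scaled Phase 2 rate, equal deaths by arm, and imputed response at the planned arm rates. The effect on the difference would be materially larger only if deaths were concentrated on CR845, and the documents give no basis for expecting that. Nothing here suggests the trial's conclusion would change. The change is worth making because it is cheap and the existing sensitivity analyses do not cover both endpoints.

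**What to change.** Add to SAP 8.2.2, after imputation and before the logistic model: for any subject who died on or before Day 85 without an observed Week 12 weekly mean (fewer than four daily scores in Days 79–85), response is set to no in all 20 datasets.

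- Apply it to the ≥3-point and ≥4-point endpoints and to Sensitivity 2 and 3. Sensitivity 1 should already have this effect.
- Apply it identically to the interim and post-interim samples in the final CHW analysis.
- Leave an observed Week 12 mean as it is, and leave the imputation for all other dropouts unchanged.

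Cost: one sentence and one programming step; date of death is already among the data to be listed (SAP 9.3). Reported response rates fall by about 1 to 2 points per arm under the assumptions above, and the final stage 1 z-score may differ slightly from the one seen at the interim. The rule does not reach the 5-D Itch and Skindex-10 analyses, which use a similar imputation (SAP 8.2.4.3) and precede the ≥4-point test.
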